**Toolkit Booster Trainings:** In addition to the initial orientation training, TK counselors will receive three brief (~30 minute) booster trainings from a TRI expert TK trainer. These sessions will focus on concrete ways that the counselors can improve their use of the Health Education Toolkit. These booster trainings will occur after the counselor has treated 1, 3, and 5 patients respectively. The counselor's checklists will be reviewed and in particular, the counselor will be provided booster training on using core homework assignments (Schedule Planning, Change Plans, and Shared Decision Making conversations).

**Treatment as Usual (TAU):** In the TAU condition, counselors will receive a control training of the same length and intensity on recovery topics that are covered in the Health Education Toolkit, but will not be immediately equipped with the Toolkit. They will then run 4 to 6 individual sessions throughout a 4 to 6-week TAU span with each of their patients enrolled in the study.

**TAU Workshop Training:** Our control training intervention compares to the TK training in that it presents new, didactic information; TAU counselors will be presented with discussion topic points on the areas covered by the Health Education Toolkit (medication facts, setting work and education goals, etc.). TAU counselors will attend a 3-hour workshop that introduces the talking points, and provides orientation on how to best to cover the talking points in therapy sessions. Counselors will be encouraged to study the talking points as they see fit to prepare to run a 4 to 6-session series over 4 to 6 weeks. Counselors will be given latitude to talk over these topics in any order they choose.

**TAU Condition:** Counselors will lead a 4 to 6-session series on similar topics over a 4 to 6-week period, but without the Toolkit aids (graphic novel volumes).

**TAU Booster Trainings:** In order to provide an attention control training that matches the amount of time that TK counselors will be trained, TAU counselors will also receive three brief (~30 minute) booster trainings from a TRI expert trainer. During these sessions, the counselor and trainer will discuss the counselor's experience running individual sessions for this study.

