## **Counselor Measures**

**Counselor Background Form (CBF):** The CBF was developed for this study and assesses the demographics and work/training histories of each participating counselor. Additionally, for this study, we have added questions on counselor's experience with medication assisted treatment. *Administered at baseline only.*

**Counselor Satisfaction Form:** The Counselor Satisfaction Form was developed for this study and assesses the extent to which counselor participants perceived the intervention to be helpful and useful. It contains both closed- and open-ended questions in order to obtain information that will help us further refine the intervention for dissemination. *Administered at 6 months only.*

**Counselor Shared Decision Making Questionnaire (SDM-Q):** The Shared Decision Making Questionnaire (SDM-Q counselor version; Simon et al., 2006) is a validated 9-item questionnaire that measures the process of shared decision making between clinicians and patients. We adapted this measure to apply to substance abuse treatment decision making. This version of the questionnaire measures shared decision making from the clinician's perspective. *Administered at baseline and 6-months.*

**Counselor Evidence-Based Practices Questionnaire:** The Evidence-Based Practices Questionnaire (Abraham et al., 2009). measures counselors' attitudes and familiarity with a range of evidence-based practices, such as MAT, CBT, and MET. *Administered at baseline and 6 months.*

**Counselor Fidelity Checklist:** The Counselor Fidelity Checklist will indicate the content areas that were covered in treatment during the intervention period. It will measure counselors' adherence to their assigned intervention, and it will help detect any between-condition contamination. *Ongoing; completed after each study treatment session.*

**8. Describe characteristics of the subject population, such as their anticipated number, age ranges, sex, ethnic background, and health status. The study should employ a study design with gender and race representation appropriate to the purpose of the research. Strong justification must be provided for exclusion of broad population groups. Identify the criteria for inclusion or exclusion. Explain the rationale for the use of vulnerable populations as research subjects (i.e., prisoners, pregnant women, disabled persons, drug users, children).**

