We will travel to the inpatient and outpatient substance abuse treatment sites in order to present the study and recruit counselor participants. After presenting the study, interested counselors can schedule a time with research staff to consent into the study. At this scheduled time, research staff will obtain written informed consent and will then administer an assessment battery as part of the Baseline Interview. Research staff will only work with treatment sites whose administrators agree that they will not impose any negative consequences on counselors who choose not to participate in the study. We then will randomly assign counselors to the toolkit (TK) or treatment-as-usual (TAU) group, and counselor participants will schedule a time to complete the initial training on their assigned condition. Counselors will be paid \$25 for measures completed at the Baseline Interview, \$75 for the initial training, \$25 for each of the 3 booster trainings, \$20 for each set of 5 fidelity checklists up to \$200, and \$25 for measures completed 6-months post Baseline Interview. Counselors can earn up to \$400 throughout the course of the study.

Client Recruitment

Immediately after a counselor completes training (either TK or TAU), we will work with the counselor to schedule a date within the next two weeks to present the study to patients who are on his or her caseload. On the scheduled day, research staff will travel to the treatment site and will present the study to those patients who attend individual therapy sessions with the counselor. Patients who are interested in the study will be asked to complete a brief verbal screening consent. We will administer the AUDIT; patients who score a 16 or above (criteria for moderate to severe alcohol use disorder) will receive further screening. We will then administer the MINI (modified for DSM-V criteria). Patients must meet criteria for current alcohol SUD (i.e., positively endorse at least 2 of the 11 items on the MINI) and have experienced 6 days of alcohol use in the past 60 days in order to be eligible. To maximize

generalizability and practical relevance of our findings, only patients who are unable to provide valid informed consent will be excluded. We expect to recruit 50 patients.

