Research staff will work with participating counselors to identify patients on their caseload who have enrolled in treatment within the past 4 weeks. Patients who are identified as potential study participants will be asked to complete a screening consent with an RA. We are requesting a waiver of written documentation of consent for the screening process. According to 45 CFR 46.117(c), written documentation may be waived if “the only record linking the subject and the research would be the consent document and the principal risk would be potential harm resulting from breach of confidentiality.” For patients who are found ineligible through the screening process, the screening consent form would be the only written document linking the patient to the research, thus a requirement for written consent would paradoxically be the only real danger to loss of privacy and confidentiality for participants who agree to be screened. We will provide an information sheet (i.e. a screening consent) to patients prior to screening that contains informed consent information, and we will obtain verbal consent that the patient is willing to participate in the screening. For patients who consent to screening, the RA will administer the AUDIT, MINI, and 8-week TLFB to determine if they meet inclusion criteria. Patients who meet the inclusion criteria and are interested in participating will be asked to provide written informed consent. Study research assistants (RAs) will fully explain the study procedures to eligible patients, and will obtain informed consent from those interested in participating.

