1. Perception of coercion: Research staff will be trained to describe the study to eligible counselors and patients, including the risks and benefits, prior to offering an invitation to participate in the study. Research staff will clearly state that the counselor's decision to participate is voluntary and will not affect their employment at the site. Similarly, we will state that a patient's decision to participate is voluntary and that it will not impact the services they receive at their treatment site. Patients will be told that treatment site staff have no vested interest in their participation and will receive no benefit if they choose to participate. All potential participants will be told that if they feel any pressure to participate from any treatment site staff, they can voice this concern to the PI or other TRI research staff, and the PI will discuss this matter with the site's director and/or other appropriate individuals.
2. Discomfort answering research questions and/or providing biological data: Individuals enrolled in any study may experience mild and transitory emotional discomfort when answering the questions posed in interviews and on questionnaires, or providing a urine sample. All participants will be informed about these possible risks before signing the consent form. In order to minimize discomfort with providing a urine sample, the sample will not be collected under observation. The research staff will complete a training regarding monitoring and addressing emotional distress among research participants, as well as an additional training on the urine collection process which will include suggestions for decreasing participant discomfort. Participants will be told that they can choose not to respond to a question that they find upsetting and can withdraw from participation at any time without negative consequence.

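### Patients are to be told that site staff gain nothing from their taking part, yet counselors, who are site staff, are paid for forms that exist only if patients take part

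*Protocol*

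**What the plan says.** Section 10 of the Protocol lists perception of coercion as its first risk. Section 11, item 1, sets out the safeguards, and one is to tell patients that "treatment site staff have no vested interest in their participation and will receive no benefit if they choose to participate".

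Four other places bear on whether that is true:

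- **Section 9, Counselor Recruitment.** Counselors receive $25 for baseline measures, $75 for initial training, $25 for each of three boosters, $20 "for each set of 5 fidelity checklists up to" $200, and $25 for the 6-month measures, with a stated maximum of $400.
- **Section 7, Counselor Fidelity Checklist.** The form is "completed after each study treatment session".
- **Section 6, Toolkit Booster Trainings.** For Toolkit (TK) counselors: "These booster trainings will occur after the counselor has treated 1, 3, and 5 patients respectively". The treatment-as-usual (TAU) text gives three boosters without that schedule.
- **Section 9, after the eligibility criteria.** "Research staff will work with participating counselors to identify patients on their caseload who have enrolled in treatment within the past 4 weeks".

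Section 6 sets 4 to 6 individual sessions per enrolled patient in both arms.

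**The concern.** The assurance is unqualified, and the payment schedule contradicts it. The counselors are recruited from the treatment sites, and section 11 itself speaks of their employment there. The sentence that follows the assurance uses the same term for site staff when it names possible sources of pressure. Nothing in the Protocol exempts counselors from that term.

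Being on a participating counselor's caseload is an inclusion criterion, and those counselors help find candidates. The inaccurate assurance thus concerns the staff member closest to the patient's decision. If the plan is followed exactly, research staff tell prospective patients something untrue, as protection against a risk the Protocol puts first. What is at stake is the accuracy of what patients are told at recruitment. No estimate or analysis is affected.

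**Working it through.** **1. Reproduce the stated maximum.** From section 9: 25 + 75 + (3 × 25) + 200 + 25 = $400. This matches the Protocol.

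**2. Separate the parts by what triggers them.**

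| Component | Amount | Needs an enrolled patient? |
|---|---|---|
| Baseline measures, initial training, 6-month measures | 25 + 75 + 25 = $125 | No |
| Fidelity checklists | up to $200 | Yes, both arms |
| Three boosters | $75 | TK: only if the patients counted are study patients. TAU: no such trigger stated |

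**3. Checklist pay per enrolled patient.** The pro rata value is $20 / 5 = $4 per checklist, so 4 to 6 sessions come to $16 to $24. Payment is by sets of five, however. If only complete sets are paid, one patient with 4 sessions brings the counselor $0, and one with 5 or 6 sessions brings $20.

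**4. Size at the planned numbers.** Inputs are 50 patients (sections 2, 4 and 9; section 8 gives 350, which does not agree, and 50 is used here), 31 counselors (sections 4 and 6) and 4 to 6 sessions (section 6).

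- Checklists: 50 × 4 = 200 to 50 × 6 = 300.
- Total pay, pro rata: 200 × $4 = $800 to 300 × $4 = $1,200.
- Patients per counselor, if spread evenly: 50 / 31 = 1.6.
- Checklists per counselor: 200 / 31 = 6.5 to 300 / 31 = 9.7.
- Pay per counselor, pro rata: $800 / 31 = $26 to $1,200 / 31 = $39.
- On complete sets only, 6.5 to 9.7 checklists make one set, or $20.

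**5. How far this is from the cap.** $200 / $4 = 50 checklists, which needs 50 / 6 = 8.3 to 50 / 4 = 12.5 patients for one counselor.

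**6. Boosters, TK only.** If the 1, 3 and 5 patients are study patients, a TK counselor with one enrolled patient also becomes due for a $25 booster, one with three for $50, and one with five for $75.

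**7. Compare with the assurance.** Patients are told of no benefit. At the planned numbers the benefit is small but above zero, and it rises with patients who join and with sessions they attend.

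**The case against.** The strongest reply is that the money is trivial and pays for paperwork. At the planned numbers it is tens of dollars per counselor, and the form is the Protocol's measure of adherence to the assigned condition. Research staff, not counselors, present the study, screen and take consent. There is a consent quiz with a 95% threshold, and patients are told they can report pressure from site staff to the investigator or research team. The counselor's stated part in recruitment is to help identify patients by date of entry into treatment. All of this stands and limits the practical risk. None of it makes a statement of no benefit true.

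A reader might infer more than the documents support:

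- **That half or more of a counselor's pay hinges on enrollment.** $200 / $400 = 50% and $275 / $400 = 69% are shares of a maximum that the planned numbers do not approach. The 69% also needs the booster trigger, which is stated for TK only. The patients it counts need not be study patients, since section 6 (Focus Groups) expects Toolkit use with clients outside the trial.
- **That coercion will be under-reported.** Section 12 counts reports of coercion, and a patient told that staff gain nothing might be slower to recognize pressure. No figure in the documents shows this, and the invitation to report pressure works against it.
- **That consent was not informed.** The consent form is not among the pages available, so whether it discloses the payments cannot be checked. If it does, it conflicts with section 11.

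**Conclusion.** The point holds as a contradiction within the current Protocol. Section 11 promises patients that site staff receive no benefit, while sections 7 and 9 together give participating counselors a payment that cannot arise unless patients take part. It rests on the checklist payment alone and applies in both arms. The TK boosters add to it only if the patients counted are enrolled in the trial.

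The size is modest: about $800 to $1,200 over the whole trial, or $26 to $39 per counselor. These figures assume 50 patients, 4 to 6 sessions each, pro rata payment and an even spread over 31 counselors. The spread will not be even, because section 6 notes that one site enrolled counselors but no clients, so some counselors earn nothing from checklists and others more than the average. The contradiction does not depend on the amount. It matters because an untrue statement serves as a participant safeguard.

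**What to change.** In section 11, item 1, and in any recruitment script or consent text that repeats it, delete the statement that site staff have no interest in and no benefit from participation. Put a true disclosure in its place: participating counselors are paid by the study for training and for forms completed after study sessions, so part of their pay depends on patients taking part and attending; declining or leaving the study will not affect the patient's care. The new text should not say that counselors' pay is independent of what the patient does, because it rises with sessions attended.

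Section 6 refers to the close of study recruitment, and its follow-up text records the funder's decision to end recruitment and close out the randomized trial. For patients already enrolled, the discrepancy should be reported to the IRB. The corrected wording should be used in any further recruitment.

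The cost is a wording change through the IRB, with no added data, visits or staff. A few patients may be put off by the disclosure. Making pay independent of enrollment would also remove the conflict, but it needs costing. Paying every counselor the full checklist amount would come to 31 × $200 = $6,200, against $800 to $1,200 under the present rule, and would end the per-form payment for the adherence measure.

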**Justify your exclusion based on one of the exclusionary circumstances listed:**

- The research topic is irrelevant for children
- Children are barred by law from participation because of the risk
- Study is redundant; knowledge is being obtained in another study or is already available
- Separate age-specific children study is preferable
- Rarity of disorder makes inclusion of children extremely difficult
- The limited number of available children are already enrolled in a nation-wide pediatric disease network
- Study design precludes direct applicability to children
- Insufficient adult data to judge potential risk for children
- Study design is a follow-up of an adult study

As the NIH definition of children includes all persons less than 21 years old, we will include children between the ages of 18 and 21 in this investigation. Based on previous enrollment in studies in the Philadelphia treatment system, we expect that 5-8% of our clients will be between the ages of 18-21. We will exclude potential participants who report that they are younger than the age of 18.

## Data Analysis Plan

**Data Management and Analysis-** All interview and self-report measures will be completed via a web-based data entry program that has been used at TRI and the University of Pennsylvania for the past 5 years. Direct data entry reduces errors that can occur when transferring information from paper forms into electronic files. See our Data Management Plan for data integrity procedures. Prior to performing analyses, standard data screening/cleaning procedures will be applied: re-screening the data for data-entry errors, assessing the extent and pattern of missing data, and checking that appropriate assumptions of normality are met, employing remedial measures when necessary. We will check to confirm that the groups do not differ at baseline on relevant background variables using analyses of variance (ANOVA) for continuous variables and log-linear models for discrete or ordinal responses. The randomization process should minimize the need for the inclusion of covariates to reduce bias in the treatment comparisons. However, relevant covariates will be considered for inclusion in the analyses to improve the precision of estimation of the effects .

**Exploratory Hypothesis 1: Patients in the TK Condition will** participate in shared decision making conversations with their counselors at higher rates than patients randomized to **TAU**. Number of sessions in which patients indicate that their counselors conducted a shared-decision making conversation at the 6-week and 3-month follow-up will be examined. Average number of sessions per patient will be compared at the 6-weeks and 3-month follow-up point. We will calculate effect sizes between conditions using Cohen's d. Quality of shared decision making conversations will be calculated using a subscale of the fidelity checklist. Differences in patient perceived quality will be averaged, and effect sizes will be calculated using Cohen's d.

**Exploratory Hypothesis 2: Patients in the TK will report greater satisfaction and acceptability with their individual sessions than patients randomized to TAU.** Scores on the Patient Satisfaction measure will be averaged and compared between conditions for the assessment at the three-month follow-up point. We will calculate overall Satisfaction rating and Satisfaction with the Referred Services Subscale score. We will calculate effect sizes using Cohen's d.

**Exploratory Hypothesis 3: Patients in the TK condition will demonstrate increased alcohol and drug abstinence (UA verified) and fewer days of self-reported alcohol and drug use during treatment and at follow-up than TAU patients.** We will compare rates of urinalysis-confirmed abstinence in the two groups at weeks 6 and 12.. The model will include terms for group, time, and their interaction, and baseline urine result along with any other necessary variables will be included as covariates. We will also compare days of self-reported alcohol and drug use based on the TLFB completed at the 6- and 12--week assessments. We will examine mean differences in abstinence rates and days of use, and estimate effect sizes using Cohen's d.

**Exploratory Hypothesis 4: Patients assigned to the TK condition will demonstrate improved ASI Alcohol Severity Scores relative to patients assigned to TAU.** We will calculate the ASI Alcohol Severity Score for patients in each condition, and examine change scores from baseline to 3-months. We will examine size of effect between condition change scores using Cohen's d.

**Exploratory Hypothesis 5: Patients assigned to the TK condition will demonstrate higher rates of engagement in substance abuse treatment than patients assigned to TAU.** Patients in the two groups will be compared on the number of treatment sessions attended in the past 90 days at the 3-month assessment. We will estimate size of effect differences on retention using Cohen's d.

**Exploratory Hypothesis 6: Patients assigned to the TK condition will demonstrate higher rates of Vivitrol initiation than patients assigned to TAU.** A logistic regression model will be used to compare patients in the two groups on initiation rates at the 3-month assessment. Patients will be considered MAT initiated if they receive a Vivitrol injection during the relevant time period, or if they attended an evaluation for Vivitrol and were deemed inappropriate for Vivitrol and referred to an alternative MAT.

**Missing Data:** As recommended by Lavori , we will analyze the data under an intent-to-treat principle in which all patients initially randomized will be included. We will characterize the group of patients who drop out before the end of the study using logistic regression models to relate dropout to these characteristics. These characteristics will be drawn from the data gathered during the study. These analyses will allow us to determine whether the drop out process is completely at random. We cannot test whether the process is missing at random (i.e. drop-out independent of values of

missed responses, conditional on covariates and observed responses), but we will attempt to obtain information on the reason for drop out. The mixed effects models will accommodate some missing data and drop out. We will examine simple pattern mixture models to assess whether the longitudinal missing data are ignorable.

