## 2. Specific aim(s)

**Aim 1:** An existing evidence-based toolkit intervention will be adapted and redesigned by a patient and provider team into an engaging, narrative graphic novel curriculum useful in substance abuse counseling. The proven behavioral interventions will be augmented with health education material focused on MAT and HIV risk reduction. Together, these materials will comprise the Health Education Toolkit. The Health Education Toolkit (**TK**) will employ a shared decision making model to encourage 1) increased recovery engagement by patients, and 2) patient engagement in deciding whether to initiate and adhere to MAT.

**Aim 2:** We will provide training and support to increase patient access to MAT for alcohol-related SUDs at a centrally located Federally Qualified Healthcare Center.

**Aim 3:** We will assess the feasibility and acceptability of the HET Toolkit to estimate whether exposure to the Toolkit (**TK**) can reduce substance use and increase engagement with MAT. We will conduct a three-month, randomized controlled trial of 50 patients with active alcohol SUDs enrolled in inpatient and outpatient treatment to obtain estimates of effect on the following exploratory hypotheses:

**Exploratory Hypothesis 1:** Patients randomized to the **TK** will participate in shared decision making conversations with their counselors at higher rates than patients randomized to treatment-as-usual sessions (**TAU**).

**Exploratory Hypothesis 2:** Patients randomized to the **TK** will report greater satisfaction and acceptability with their individual sessions than patients randomized to **TAU**.

**Exploratory Hypothesis 3:** Patients randomized to **TK** treatment sessions will demonstrate a) larger reductions in substance use (drug and alcohol) and b) increases in abstinence measured by urine-confirmed, self-reported days using over the 3-month follow-up compared to patients randomized to **TAU**.

**Exploratory Hypothesis 4:** Patients assigned to the **TK** condition will demonstrate improved ASI Alcohol Severity Scores relative to patients assigned to **TAU**.

**Exploratory Hypothesis 5:** Patients randomized to **TK** will attend more specialty substance abuse intervention and treatment sessions over the 3-month follow-up period than patients randomized to **TAU**.

**Exploratory Hypothesis 6:** Patients randomized to **TK** will initiate MAT for alcohol dependence at greater rates than patients randomized to **TAU**.

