**Patient Outcomes**

Quick Drinking Screen and ASI Drug Grid: This instrument contains items from two established instruments: the Quick Drinking Screen (QDS), and the Addiction Severity Index (ASI). The QDS is a six question screener that estimates the frequency and quantity of drinking. Two comparison studies found high levels of agreement between the QDS and the Timeline Followback, the “gold standard” in drinking measurement (Roy et al. 2008, Sobell et al, 2003). We also included the Follow-up Assessment Drug Grid and overall drug use questions from the ASI (see below) in order to assess for both alcohol use and other substance use. *Administered at 6 weeks only*.

Urine testing: Urine drug testing will be done using kits that test for cocaine, opiates, amphetamines, methamphetamines, benzodiazepines, cannabis, barbiturates, and PCP. These will be purchased from ACON International. These kits provide a rapid (5-minute) on-site urine test. *Administered at BL, 6 weeks, 3 months, 6 months*.

Non-Study Medical and Other Services (NSMOS): This questionnaire was adapted from the Treatment Services Review (McLellan et al., 1992) for patients in medical settings. The NSMOS counts substance abuse treatment, medical services, visits to medical offices, hospitalizations, and emergency room visits received that were not a part of the assigned treatment. *Administered at BL, 6 weeks, 3 months, 6 months*.

PHMC Utilization Review: PHMC Care Clinic will maintain records on patients from the study who are referred for Vivitrol evaluation. By prior patient consent, the Care Clinic will release records on whether a study patient attended an appointment for a Vivitrol evaluation, the determination of appropriateness for Vivitrol, and whether the patient actually received the initial dose and subsequent doses (if any) of medication.

HIV Risk Assessment (HIV-RA): The HIV Risk Assessment provides a brief self-report measure of HIV testing history and sexual risk and uses the preceding three months as the time interval of interest. The HIV-RA was developed [name], and [name], experts in the field of HIV risk behaviors. *Administered at BL, 6 weeks, 3 months, 6 months*.

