#### Inclusion and Exclusion Criteria

*Inclusion Criteria:* (a) patient is on the caseload of a participating counselor, (b) patient is 18 years or older, (c) a screening score of at least 16 on the AUDIT, (d) patient meets criteria for a substance use disorder as defined by DSM-V assessed via the MINI Plus 5.0, (i.e., endorsement of at least 2 of the 11 items on the MINI), (e) the patient has enrolled in the treatment program within 4 weeks prior to the date of consent and (f) patient reports 6 days of alcohol use in the past 60 days. Each participant must meet all the inclusion criteria in order to be enrolled in the study.

*Exclusion Criteria:* (a) the patient reports plans to leave the Philadelphia greater metropolitan area within the next 6 months; (b) the patient is not English-speaking; (c) the patient is mandated to attend inpatient treatment (i.e. considered a prisoner), or (d) if the patient is unable to provide valid informed consent by correctly describing the key components of consent to the RA.

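### Exploratory Hypothesis 3 claims urine-verified alcohol abstinence, but the urine kits do not test for alcohol; its follow-up source for days of use is also not in the protocol's schedule

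*SAP*

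**What the plan says.** **Abstinence.** SAP Exploratory Hypothesis 3 reads: "Patients in the TK condition will demonstrate increased alcohol and drug abstinence (UA verified) and fewer days of self-reported alcohol and drug use". The analysis that follows is: "We will compare rates of urinalysis-confirmed abstinence in the two groups at weeks 6 and 12". On covariates the SAP adds: "baseline urine result along with any other necessary variables will be included as covariates". Protocol section 2 words its own Exploratory Hypothesis 3, which covers both drugs and alcohol, as "increases in abstinence measured by urine-confirmed, self-reported days using over the 3-month follow-up".

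**Urine test.** Protocol section 7, Patient Outcomes, states: "Urine drug testing will be done using kits that test for cocaine, opiates, amphetamines, methamphetamines, benzodiazepines, cannabis, barbiturates, and PCP".

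**Days of use.** The SAP states: "We will also compare days of self-reported alcohol and drug use based on the TLFB completed at the 6- and 12--week assessments". Protocol section 7 schedules different follow-up instruments: the Quick Drinking Screen (QDS) with the ASI drug grid at 6 weeks only, and the modified ASI-6, which contains QDS items, at baseline, 3 months and 6 months. Protocol section 9 has a research assistant give an 8-week TLFB at screening, to establish eligibility.

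**Population.** The inclusion criteria in protocol section 9 require "a screening score of at least 16 on the AUDIT" and that the "patient reports 6 days of alcohol use in the past 60 days".

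**The concern.** Alcohol is the target substance. Every participant must pass two alcohol criteria, and no criterion requires use of a drug on the urine panel. A participant who only drinks can be negative on the panel at every visit, baseline included. A report that followed the SAP's wording would claim biological verification of alcohol abstinence that the study had no means of making.

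There is a practical consequence as well. Neither document gives the rule that turns self-report and urine into abstinent or not abstinent, so two analysts could code the outcome differently and both follow the text. For days of use, the analyst is sent to an instrument that the protocol does not schedule at follow-up.

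The hypothesis is exploratory, but protocol section 5 says that the purpose of the preliminary data is to establish effect sizes from which a later, fully powered trial will be sized. What each estimate measures, and from which instrument, should therefore be unambiguous.

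**Working it through.** There is no figure in the plan to reproduce, so the check sets the relevant texts side by side.

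**Step 1: what the urine test can verify.** The kit analytes listed in protocol section 7 are:

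1. cocaine
2. opiates
3. amphetamines
4. methamphetamines
5. benzodiazepines
6. cannabis
7. barbiturates
8. PCP

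Alcohol or an alcohol metabolite: 0 of 8. The remaining patient measures in section 7 are questionnaires, interviews, checklists and clinic records. No breath test or other alcohol biomarker is among them. A urine result from this study can support or contradict a report about the eight classes and says nothing about drinking.

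**Step 2: how abstinence could be scored.** The scoring rule is not written down, so take the two candidate rules in turn for a participant who drinks and has no listed drug in the urine.

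| Rule | Admits drinking | Does not disclose drinking |
|---|---|---|
| Self-report, checked by urine | Not abstinent (correct) | Abstinent (undetected) |
| Urine alone | Abstinent (wrong) | Abstinent (wrong) |

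Under the first rule the panel adds nothing for alcohol, but admitted drinking still counts, so the estimate may stand as a self-reported outcome. Under the second rule the outcome would not measure drinking at all. Under both, calling the alcohol part verified is untrue.

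**Step 3: the baseline covariate.** The baseline urine result carries no alcohol information, for the reason in step 1. The SAP also allows other necessary variables, so baseline drinking can be included. The covariate sentence is therefore incomplete for alcohol rather than wrong.

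**Step 4: source of days of use.**

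| Time | SAP Hypothesis 3 | Protocol |
|---|---|---|
| Screening | not mentioned | 8-week TLFB (section 9) |
| Baseline | not mentioned | modified ASI-6 with QDS items (section 7) |
| 6 weeks | TLFB | QDS and ASI drug grid (section 7) |
| 12 weeks / 3 months | TLFB | modified ASI-6 with QDS items (section 7) |

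The labels 12 weeks and 3 months are taken as the same visit. Follow-up visits at which the protocol schedules a TLFB: 0. Its only other mention in the protocol's description of measures is as the standard against which the QDS was compared. Self-reported use is collected at both follow-up visits, so the problem is an unreconciled source and not an absence of data. Section 7 does not give the look-back windows of the QDS and ASI use items, or say how days of use would be derived from them.

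**The case against.** A reader might infer from the SAP's references to urinalysis and from the baseline urine covariate that abstinence is scored from urine alone, so that the effect estimate is seriously wrong. The documents do not support that. No text says that urine alone decides the score. Protocol Hypothesis 3 makes self-reported days the measure and urine the confirmation, and words such as verified and confirmed presuppose a report that is being checked. A baseline urine covariate fits a combined outcome just as well. On this reading an admitted drinker is not abstinent. This objection stands, and it limits the consequence.

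It is also fair to say that drinking is measured without urine elsewhere: by self-reported days of use within Hypothesis 3 and by the ASI alcohol score in Hypothesis 4. The hypothesis is one of six exploratory ones in a feasibility study, and section 5 of the protocol does not say that abstinence will be the outcome used to size the later trial. That stands too.

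One could argue that the urine label was meant for drugs only. The SAP attaches it to alcohol and drug abstinence together and defines alcohol abstinence nowhere else, so that intention cannot be read from the text.

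Finally, the protocol does use a TLFB. It does so at screening, before enrolment, which does not supply data for 6 or 12 weeks.

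**Conclusion.** The plan is wrong as written on both points and should be corrected. Alcohol abstinence cannot be verified by the listed urine test (0 of 8 analytes), although the SAP says that it is and the protocol's wording implies it. The SAP's follow-up TLFB does not match the protocol's schedule; the documents do not settle which is right.

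The size of any bias is unknown. It would depend on the scoring rule, on how many participants have drug-negative urine and on how many of those drink, and the documents give none of these. Under the reading that protocol Hypothesis 3 favours, the bias from scoring may be nil and the fault is confined to the claim of verification. The conclusion rests on section 7 being the complete list of measures. If an alcohol biomarker or a follow-up TLFB was in fact collected, the corresponding part is resolved by adding it to the documents.

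**What to change.** 1. In SAP and protocol Hypothesis 3, restrict the urine-verified and urine-confirmed wording to the listed drugs. Score drug abstinence at each visit as no self-reported drug use together with a negative panel.
2. Define alcohol abstinence separately, from the self-report items collected at each visit. Label it self-reported and not biologically verified, and state that a urine result alone never scores a participant as alcohol-abstinent. Name baseline self-reported drinking as its baseline covariate.
3. Reconcile the TLFB with the protocol's schedule. Either name in the SAP the QDS and ASI items that supply days of use at 6 weeks and 3 months, with their look-back windows, or, if a follow-up TLFB was given, add it to the protocol's measures with its timing.

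The cost is a few sentences in each document, a short scoring rule and a list of items and windows. No test or visit is added. The downside is that the alcohol result then rests openly on self-report alone, which is a weaker claim, and undisclosed drinking remains undetected.
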